- b) Subjects who have no tumor assessment after randomization will have PFS censored at the date of randomization, unless they died before the second scheduled tumor assessment.

Further details and other cases will be described in the statistical analysis plan (SAP).

Analysis of Secondary Endpoints

The secondary endpoints (OS, ORR, and DoR) will be analyzed using the investigator and independent radiological review assessments. The degree of agreement between the investigator and the independent assessment of responses will also be summarized and presented in a table.

The first secondary analysis will compare the OS between the 2 treatment arms by using stratified Log-rank test and the stratification factors included in the primary analysis. An interim OS analysis will be carried out at the time of the Final PFS analysis.

Duration of response (DoR) will be analyzed using the same method as for the progression-free survival.

The proportion of subjects achieving confirmed ORR (complete response [CR]+partial response [PR]) will be summarized and presented by treatment arms and cycle and will be compared between the two treatment arms using Cochran-Mantel-Haenszel (CMH) test with the same stratification factors used for the PFS analysis.

Exploratory Analyses

In order to evaluate if the timing of post-baseline radiological scan influenced the primary outcome, the time from randomization to post-radiological scan will be calculated and an exploratory analyses will be conducted. Means and standard deviation of radiological scan time will be presented by treatment arms and cycle time. Log-rank test will be used to test if cumulative percentages (survival curves) are equal (median time to each cycle from randomization) by treatment arms.

Subgroup Analyses

PFS subgroup analyses by gender, race, and age (< 65 years and \geq 65 years) will be carried out using separate unadjusted Log-rank test for the ITT population.

Definition of Efficacy Endpoints

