Progression-Free Survival (PFS) is defined as the time from randomization to first documentation of objective tumor progression (progressive disease [PD], radiological) according to RECIST (Version 1.1) or death due to any reasons whichever comes first. PFS data will be censored on the day following the date of last tumor assessment documenting absence of PD for subjects who do not have objective tumor progression and are still on study at the time of the analysis, are given anti-tumor treatment other than the study treatment, or are moved from treatment follow-up prior to documentation of objective tumor progression. Subjects having no tumor assessments after randomization who are not known to have died will have PFS censored on the date of randomization.

Overall survival (OS) is defined as the time from the date of randomization to date of death due to any cause. In the absence of confirmation of death, survival time will be censored at the last date the subject is known to be alive. Subjects lacking data beyond randomization will have their survival times censored on the date of randomization.

Overall response rate (ORR) is defined as the proportion of subjects with confirmed CR or confirmed PR according to RECIST (Version 1.1), relative to the total population of randomized subjects. Confirmed responses are those that persist on repeat imaging study at least 4 weeks after the initial documentation of response.

Duration of response (DoR) is defined as the time from the first documentation of objective tumor response to the first documentation of objective tumor progression or to death due to any cause. DoR data will be censored on the day following the date of the last tumor assessment documenting absence of PD for subjects who do not have tumor progression and are still on the study at the time of an analysis, are given antitumor treatment other than the study treatment, are removed from the study follow-up prior to documentation of objective tumor progression, died of non-cancer related cause, including death due to unknown cause in the absence of documented disease progression. **DoR will only be calculated for the subgroup of subjects with an objective tumor response (PR or CR).**

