3.2 Efficacy and Safety Variables

3.2.1 Efficacy Variables

Tumor response will be assessed using RECIST v1.1 criteria. Subjects will undergo assessments at screening and every 8 weeks following Cycle 1, Day 1 until radiological disease progression is documented and confirmed by independent radiology review. Evaluable subjects are those who receive at least 2 cycles of study drug.

Best overall response (BOR) is determined once all assessments from randomization until disease progression or death are recorded. In general, it is the best response across all assessments; however, confirmation of complete response (CR), partial response (PR), and stable disease (SD) will also be used in BOR determination. To confirm CR or PR changes in tumor measurements must be confirmed by repeat assessments that should be no less than 4 weeks (28 days) after the criteria for response are first met. To confirm SD, it must have occurred at least 8 weeks from Cycle 1, Day 1; otherwise, BOR will depend on subsequent assessments.

All subjects will be followed until death from any cause (unless the subject is lost to follow-up, withdraws consent for the entire study, or the sponsor terminates the study early). After the 30-Day Follow-up visit, subjects will be contacted once every 3 months by the site to collect long-term survival data. For subjects with ongoing objective response or disease stabilization at the time of treatment discontinuation, or for subjects who discontinue for reasons other than radiological evidence of progressive disease, tumor assessments will continue to be collected every 2 months during the first year (beginning from the date of the last scan performed prior to treatment discontinuation), every 3 months during the second year, and every 6 months thereafter until disease progression is confirmed by independent radiology review or the start of another anti-tumor therapy that includes anti-cancer surgery/procedure, anti-cancer radiotherapy, and anti-cancer systemic therapy.

Primary Efficacy Endpoint

PFS is defined as the time from randomization date to the first date of radiological PD or death date (due to any reason), whichever event is earlier. PFS in months will be calculated as: (first event date – randomization date + 1) * (12/365.25). Censoring will occur as follows:

- If there are no tumor assessments after randomization, PFS will be censored on the date of randomization.

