- If a subject is known to be alive and progression-free, PFS will be censored on the day of the last tumor assessment.
- If a subject is given anti-tumor treatment (anti-cancer surgery/procedure, anticancer radiotherapy, and anti-cancer systemic therapy other than the study treatment) prior to PD or death, PFS will be censored on the date of the last tumor assessment prior to the start date of the anti-tumor treatment.
- If treatment follow-up ceases prior to objective PD, PFS will be censored on the date of the last tumor assessment.

Secondary Efficacy Endpoints

OS is defined as the time from the date of randomization to the date of death (due to any reason). OS in months will be calculated as: (death date – randomization date + 1) * (12/365.25). Censoring will occur as follows:

- If there are no tumor assessments after randomization, OS will be censored on the date of randomization.
- If there is no confirmation of death, OS will be censored on the date the subject is last known to be alive.

ORR is defined as the proportion of subjects with best overall response (BOR) of confirmed CR or confirmed PR [i.e. objective response (OR)], according to the RECIST 1.1 among subjects with measurable disease at baseline.

DoR is defined as the time from the first date of OR to first date of radiological PD. This will only apply to subjects with confirmed CR or confirmed PR and will be calculated as: (first event date – first OR date + 1) * (12/365.25). Censoring will occur as follows:

- If a subject is known to be alive and progression-free, DoR will be censored on the day following the date of the last tumor assessment.
- If a subject dies of a cause known to be non-cancer related, DoR will be censored on the date of the last progression-free tumor assessment.
- If a subject dies of an unknown cause in the absence of documented PD, DoR will be censored on the date of the last tumor assessment.
- If a subject is given anti-tumor treatment (anti-cancer surgery/procedure, anticancer radiotherapy, and anti-cancer systemic therapy other than the study

treatment) prior to PD or death, DoR will be censored on the date of the last progression-free tumor assessment prior to the start date of the anti-tumor treatment.

• If treatment follow-up ceases prior to objective PD, DoR will be censored on the date of last progression-free tumor assessment.

Tertiary Efficacy Endpoint

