4.7.2 Primary Efficacy Variable – PFS

Primary Analysis on PFS

The primary variable for the assessment of efficacy is PFS, as defined in Section 3.2.1 of this SAP.

PFS based on IRR will be summarized for the ITT population using the Kaplan-Meier method. These summaries will include 1- and 2-year survival probabilities along with corresponding 95% CIs. Graphical displays (i.e. K-M plots), where appropriate, will also be produced.

Median event times and corresponding two-sided 95% CIs for the medians will be provided for PFS. A stratified log-rank test (one-sided, α =0.025) as well as hazard ratios and corresponding 95% CIs from a stratified Cox proportional hazard model, both adjusting for IMDC risk category and prior therapy, will be used to compare PFS between the two treatment arms.

When determining PFS, the recorded date of progression (defined as first time at which progression can be declared) will be used. For progression due to the presence of a new lesion, the date of progression is the first date that the new lesion was observed. If multiple assessments based on the sum of target lesion measurements are done at different times, the date of progression is the date of the last observation or radiological assessment of target lesions that shows a predefined increase in the sum of the target lesion measurements.

The robustness of the study results to the choice of baseline covariates will be investigated as described in Section 4.7.1.2. In addition, the homogeneity of the treatment effect for important subgroups will be investigated as described in Section 4.7.1.6.

A by-subject listing of the primary efficacy data will be provided.

Sensitivity Analyses on PFS

Sensitivity Analysis #1 will be done using the investigator assessment of response, adding in as events any clinical PDs specified by the investigator. A clinical PD is defined to be treatment failure not meeting the criteria for progressive disease but considered by the investigator to require removal of the subject from the study. This analysis will be conducted using the ITT and PP populations.

Sensitivity Analysis #2 will consider the initiation of new anti-tumor treatment to be an event. In this analysis, any death or PD will also be events, even those that occur after two or more missed tumor assessments. This analysis will be conducted using only the ITT population.

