4.9 Determination of Sample Size

A sample size of 322 subjects (161 subjects per treatment arm) with a total number of 255 events will provide 90% power to detect a statistically significant difference between treatment arms with respect to PFS as assessed by the IRR. The sample size was determined based on the following assumptions:

- The distribution of the PFS for the two treatment arms will be compared by using a log-rank test with one-sided 2.5% significance level.
- The median PFS for subjects receiving sorafenib and tivozanib is 4 months and 6 months, respectively (an increase of 2 months or 50%).
- An equal number of subjects will be assigned to each treatment arm.
- Enrollment will take 15 months.
- The drop out percentage per treatment arm will be 3%.

The first secondary analysis will compare OS between sorafenib and tivozanib by using a stratified log-rank test (stratification factors included in the primary analysis), and twosided 0.8% significance level (utilizing a Lan-DeMets alpha spending function with an O'Brien Fleming boundary). The interim OS analysis will be done at the time of the final PFS analysis. Assuming a median OS for sorafenib of 12 months and a median OS for tivozanib of 16 months, 245 OS events at the time of final OS analysis and 149 OS events at the time of final PFS analysis will yield approximately 61% power to demonstrate longer OS for tivozanib using the log-rank test, given 2.5% type I error (one-sided). The final OS analysis will be performed when all subjects have been lost to follow-up, have withdrawn consent, have died, or when all subjects in follow-up have been on-study for at least 2 years, whichever occurs first.

The estimate was obtained by using East® statistical package Version 6.3 by Cytel Inc.

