4.10 Changes in the Conduct of the Study or Planned Analysis

Protocol Version 4.0 was finalized on 01 October 2018. The administrative change was:

• A previously unspecified data cut-off date for the primary analysis was established to be 04 October 2018 with a targeted number of 242 PFS events.

The PFS event rate continues to decelerate. The study steering committee participated in a conference call on Thursday, August 30, 2018 and unanimously recommended performing the analysis rather than waiting for the additional events to reach the planned 255 PFS events. The reasons given were that the current patients have been on study for at least one year and may not progress for some time, and that the small reduction in events at the time of final analysis was unlikely to materially affect the results.

- The committee was concerned that based on the small number of patients remaining that can contribute to a PFS event, it could take another 5 months or more to get to 255 events.
- Some committee members expressed that based on the safety profiles they have observed during the study, they are keen to provide access to this drug to their patients.

This proposal was presented to the US FDA and they reported the decision is at the discretion of the Steering Committee and the sponsor.

Protocol Version 3.0 was finalized on 13 July 2016. Changes that have statistical implications are:

- the removal of the tertiary objective of exploring the correlation of serumneuropilin 1 (NPR-1) with clinical activity in subjects randomized to treatment with tivozanib or sorafenib.
- The addition of the tertiary objectives of exploring the relationship between tivozanib and sorafenib drug levels and activity as well as the relationship between the IP drug levels and AEs.

Subjects must begin planned treatment of the study drug within 14 days after randomization.

An exploratory analysis of PFS on the safety population was added to the SAP to account for subjects that were randomized to a treatment arm but not dosed due to external issues.

Best Overall Response criteria was updated to align with the RECIST 1.1 guidelines.

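### SAP 3.2.1 censors PFS at randomization for every subject without a post-randomization scan, even one known to have died, and a parallel OS bullet does the same to known deaths

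*SAP*

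**What the plan says.** SAP 3.2.1 defines PFS as time from randomization to radiological progression or death from any cause. Its first censoring bullet is "If there are no tumor assessments after randomization, PFS will be censored on the date of randomization".

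Protocol 14.3.4 handles the same subjects differently, in two places. Under Handling of Missing Data, item (b) censors subjects without a post-randomization assessment at randomization "unless they died before the second scheduled tumor assessment". Under Definition of Efficacy Endpoints the rule is: "Subjects having no tumor assessments after randomization who are not known to have died will have PFS censored on the date of randomization".

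For OS, SAP 3.2.1 has a parallel bullet: "If there are no tumor assessments after randomization, OS will be censored on the date of randomization". The protocol's OS rule is narrower: "Subjects lacking data beyond randomization will have their survival times censored on the date of randomization". All other subjects not confirmed dead are censored when last known alive.

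SAP 4.10, which lists changes to the planned analysis, mentions neither difference.

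**The concern.** The protocol and SAP assign different records to the same subject in the primary endpoint and in the first secondary endpoint, and two programmers could code them differently. Followed literally, the SAP removes real events and contradicts its own definitions of PFS and OS. The trial is open-label, so a choice made after results are seen would be a data-informed one.

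The group is not hypothetical. SAP 4.10 mentions "subjects that were randomized to a treatment arm but not dosed due to external issues". Scans are scheduled from Cycle 1 Day 1, so these subjects have no scheduled post-randomization scan, yet SAP 4.4 keeps them in the ITT population. Their number is not given.

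No planned analysis isolates the rule. In Sensitivity Analysis #2 (SAP 4.7.2) "any death or PD will also be events, even those that occur after two or more missed tumor assessments", but that analysis also makes new anti-tumor therapy an event. Its wording further implies that the primary analysis has a missed-assessment rule, which SAP 3.2.1 never states. No sensitivity analysis is planned for OS.

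**Working it through.** **Rules side by side, for a subject with no scan after randomization and no new anti-tumor therapy**

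| Subject | Protocol 14.3.4, missing data (b) | Protocol 14.3.4, definitions | SAP 3.2.1, literal |
|---|---|---|---|
| PFS, alive | censored day 0 | censored day 0 | censored day 0 |
| PFS, died before second scheduled scan | exempt from day-0 censoring | event | censored day 0 |
| PFS, died later | censored day 0 | event | censored day 0 |
| OS, alive with follow-up | not covered | censored when last known alive | two bullets conflict: day 0 or last known alive |
| OS, died | not covered | event | censored day 0 |

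**The plan's own figures.** Inputs are from SAP 4.9: PFS medians 4 and 6 months (HR 4/6), 161 per arm, one-sided 2.5%; OS medians 12 and 16 months (HR 0.75). Schoenfeld power is Φ(|ln HR|·√D/2 − 1.96).
- PFS, D = 255: 89.9%, against 90% stated.
- PFS, D = 242 (the targeted number in SAP 4.10): 0.4055 × 15.556/2 − 1.96 = 1.194, so 88.4%.
- OS, D = 245, ignoring the interim look: 61.5%, against about 61% stated.

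**Deaths before the first scan.** The documents give no early-death rate. Assume exponential OS at the planned medians. The first scan falls at day 56 (1.84 months), or at day 70 (2.30 months) if treatment starts 14 days after randomization, the limit in Protocol 5.1.
- Day 56: 161·(1 − exp(−ln2·1.84/12)) = 16.2 on sorafenib; 161·(1 − exp(−ln2·1.84/16)) = 12.3 on tivozanib; total 28.6 (unrounded).
- Day 70: 20.0 + 15.3 = 35.3.
- At a quarter of the hazard: 7.4 and 9.2.

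**First PFS events lost.** Only a death that precedes progression is a lost PFS event. With PFS hazard h and death hazard d inside it, the expected loss per arm is 161·(d/h)·(1 − exp(−h·t)). At day 56 and full hazard, sorafenib loses 161·(4/12)·(1 − exp(−0.3188)) = 14.65 and tivozanib 161·(6/16)·(1 − exp(−0.2125)) = 11.56, total 26.2.

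The simulation used 12,000 trials per row, uniform 15-month accrual and a cut-off at the 242nd true event, with those deaths recoded as censored at day 0:

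| First scan, hazard | Lost (sorafenib + tivozanib) | 242 less lost | Schoenfeld power | Simulated HR | Simulated power |
|---|---|---|---|---|---|
| Day 56, quarter | 3.7 + 2.9 = 6.6 | 235.4 | 87.5% | 0.667 → 0.664 | 87.6% → 87.2% |
| Day 70, quarter | 4.4 + 3.5 = 7.9 | 234.1 | 87.3% | 0.666 → 0.662 | 88.1% → 87.6% |
| Day 56, full | 14.7 + 11.5 = 26.2 | 215.8 | 84.6% | 0.667 → 0.657 | 88.2% → 86.7% |
| Day 70, full | 17.7 + 14.1 = 31.8 | 210.2 | 83.6% | 0.667 → 0.652 | 87.5% → 86.2% |

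Simulated power falls less than Schoenfeld power because the HR moves away from 1. If the 242 events were counted under the SAP rule, power stays at 88.4%.

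**An assumed imbalance.** With extra early tivozanib deaths (day 56, quarter hazard otherwise), losing about 4 sorafenib and 6 tivozanib deaths moves the HR from 0.687 to 0.665; losing about 4 and 10 moves it from 0.714 to 0.668.

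**OS.** The final analysis is triggered by follow-up and not by a death count: "when all subjects in follow-up have been on-study for at least 2 years, whichever occurs first". Lost deaths are therefore not replaced. Single-look power is 61.5% at 245 deaths, 60.2% at 238 (245 − 7.4, rounded) and 55.0% at 210 (245 − 35.3, rounded).

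**The case against.** The best defence is that SAP 3.2.1 defines the event first, so the censoring bullets apply only to subjects without one. The fourth PFS bullet supports this: it censors at the last assessment when follow-up ends before objective progression, and taken literally it would censor every death without progression. The SAP also says so outright when it means to censor deaths, as in the DoR rules, and SAP 4.7.1.3 handles deaths in OS by date and never by scan status.

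That reading is plausible but is not in the text. Neighbouring bullets carry conditions (known alive and progression-free; no confirmation of death), while the no-scan bullets carry none. The new-therapy bullet does override later events, so precedence of events cannot be inferred. For OS the defence fails even if granted: an unscanned survivor would still be censored at day 0 instead of when last known alive.

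Several counterpoints stand:
- The expected effect is small.
- The full-hazard rows require every death before week 8 or 10 to be unscanned and to occur at the full exponential rate. ECOG 0 or 1 and a life expectancy of at least 3 months at entry (Protocol 6.1), together with End-of-Treatment scans (Protocol 7.1.7), make the lower rows more plausible.
- The imbalance scenario is an assumption.
- The direction of bias does not simply follow the arm with more early deaths. Under the plan's assumptions sorafenib loses more, yet the HR moves in tivozanib's favour, because the removed deaths have a ratio (0.75) closer to 1 than the PFS HR (0.667).
- For PFS, undosed subjects matter only if they die unscanned without new therapy.
- The fourth PFS bullet has the same gap.

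**Conclusion.** The concern holds. SAP 3.2.1 contradicts its own event definitions and the protocol for subjects who die without a scan, in both PFS and OS, and the change is undeclared. The OS bullet is the harder to defend, since it discards known deaths from a survival endpoint and conflicts with the bullet that follows it.

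Under exponential survival at the planned medians, the PFS loss costs 0.4 to 1.5 points of simulated power, and up to 4.8 points by Schoenfeld (88.4% to 83.6%) at the full hazard. The HR shift is at most 0.015. These are not bounds, because a never-scanned subject can also die later. Larger HR shifts need an imbalance that the documents neither give nor rule out. Correction is required because the definitions conflict, whatever the likely bias.

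**What to change.** In SAP 3.2.1, replace the PFS bullet with: *A subject without any post-randomization tumor assessment has PFS censored at randomization, unless the subject died without having started new anti-tumor treatment; that death is a PFS event on its date.* This follows the broader of the two protocol exceptions. If the narrower one is chosen, add its time limit.

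Replace the OS bullet with: *Only subjects with no data after randomization have OS censored at randomization. A known death is always an OS event, subject only to the partial-date rules in SAP 4.7.1.3.*

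Reconcile item (b) of Protocol 14.3.4 with the PFS definition in the same section, so that one rule decides which unscanned deaths count. State in both documents whether the primary analysis has the missed-assessment rule that Sensitivity Analysis #2 implies and, if so, what it is. Make clear that the fourth PFS bullet does not override a death.

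The cost is two rewritten SAP bullets and these clarifications before database lock, plus an administrative protocol correction or a declared change in SAP 4.10. It needs no new data and no change to the sample size.

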Sensitivity Analysis #3 will be similar to Sensitivity Analysis #2, with the addition of discontinuation of therapy considered an event as well. Again, this analysis will be conducted using only the ITT population.

Sensitivity Analysis #4 will be conducted to assess the impact of missed or not evaluable (NE) tumor assessments. This analysis will use the IRR assessments and backdate any PD events that occur immediately after missing or NE assessments. If the PD occurs immediately after NE assessment (or series of NE assessments), the PD date will be the date of the first NE assessment preceding the PD. If the PD occurs immediately after a missed assessment (or series of missed assessments), the PD date will be the date of the first missed assessment preceding the PD. This analysis will use the ITT population.

All sensitivity analyses will use the same statistical methods as the primary analysis.

Exploratory Analysis on PFS

An exploratory analysis of PFS based on IRR will be summarized for the SAF population using the Kaplan-Meier method. This analysis will examine PFS for all subjects who were randomized and administered at least one dose of the study drug. This analysis will use the same statistical methods as the primary analysis.

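### The SAP's three scan-based PFS censoring bullets omit the protocol's condition that the last tumor assessment must document absence of PD

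*SAP*

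**What the plan says.** Protocol 14.3.4 covers three situations in one sentence: no PD and still on study, other anti-tumor treatment given, and follow-up ended before PD. In each, "PFS data will be censored on the day following the date of last tumor assessment documenting absence of PD".

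SAP 3.2.1 gives each situation its own bullet:

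1. Alive and progression-free: "If a subject is known to be alive and progression-free, PFS will be censored on the day of the last tumor assessment".
2. New anti-tumor treatment: "PFS will be censored on the date of the last tumor assessment prior to the start date of the anti-tumor treatment".
3. Follow-up ends: "If treatment follow-up ceases prior to objective PD, PFS will be censored on the date of the last tumor assessment".

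None of these says what the scan must have shown. A separate bullet censors at randomization when there is no post-randomization assessment at all.

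The DoR bullets in the same section are mixed. The counterpart of bullet 3 reads "If treatment follow-up ceases prior to objective PD, DoR will be censored on the date of last progression-free tumor assessment". The DoR bullets for new treatment and for non-cancer death also require a progression-free scan. The DoR bullets for subjects alive without progression and for death of unknown cause do not.

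Primary PFS is IRR-based (SAP 4.7.2). NE is a recognised outcome, both in the response table of Protocol Appendix A and in SAP 4.7.2, where "Sensitivity Analysis #4 will be conducted to assess the impact of missed or not evaluable (NE) tumor assessments". SAP 4.10, which records changes to the planned analysis, does not mention PFS censoring.

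**The concern.** PFS should be censored at the last date on which the subject was shown to be free of progression. If the final scan is NE, that date is the scan before it. An unqualified last assessment lets a programmer use the NE scan instead, which adds unobserved time at risk to the primary endpoint. Bullets 2 and 3 are the clearest cases, because their DoR counterparts a few lines below keep the condition.

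The gap also reaches a subject whose only post-baseline scans are NE. That subject has had an assessment, so the randomization-date bullet does not literally apply, although absence of PD was never documented after baseline.

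If NE last scans were equally common in both arms, the extra time would largely cancel in the hazard ratio. If they were not, the HR would move towards the arm with more of them. The trial is open-label and the documents do not say how often scans are NE.

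**Working it through.** **Design figure.** Inputs from SAP 4.9: medians 4 and 6 months, 1:1 allocation, one-sided 2.5%, 90% power. With exponential PFS the HR is 4/6 = 0.667. Schoenfeld: d = 4(1.960 + 1.282)² / (ln 1.5)² = 255.7, so 256 against the stated 255. Power at 255 events is Φ(√255 × 0.4055/2 − 1.960) = 0.899. At the 242 events targeted in SAP 4.10 it is 0.884. The plan's figure reproduces, and none of these inputs involves the censoring date.

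**Subjects exposed to the rule.** Censored: 322 − 255 = 67 at the planned count, or 322 − 242 = 80 at the cut-off target. With an assumed 10% to 30% of last scans NE, 80 × 0.10 = 8 to 80 × 0.30 = 24 subjects are affected.

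**Time added.** On treatment, scans are "every 8 weeks following Cycle 1, Day 1": 56 × 12/365.25 = 1.84 months. End-of-treatment scans (Protocol 7.1.7) and unscheduled scans (Protocol 7.1.9) can follow the previous scan sooner. Off treatment, SAP 3.2.1 spaces scans at 2 months in the first year, then 3, then 6.

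**Effect on the HR.** Simulation, 1,500 runs per row, unstratified log-rank, 161 per arm. Assumptions not in the documents: exponential PFS, uniform 15-month accrual, cut-off at 27 months, scanning stops at a hazard of 0.03 per month, scans on an exact 8-week grid, and the last scan NE with the stated probability regardless of true status. The HR is a one-step estimate and sits below 0.667, so only the contrast between rules matters.

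| NE sorafenib / tivozanib | True HR | HR, SAP rule | HR, protocol rule | Rejection, SAP | Rejection, protocol |
|---|---|---|---|---|---|
| 10% / 10% | 0.667 | 0.629 | 0.628 | 0.884 | 0.884 |
| 30% / 30% | 0.667 | 0.629 | 0.626 | 0.873 | 0.873 |
| 10% / 30% | 0.667 | 0.614 | 0.627 | 0.897 | 0.873 |
| 30% / 10% | 0.667 | 0.643 | 0.627 | 0.833 | 0.869 |
| 10% / 30% | 1 | 0.973 | 0.994 | 0.039 | 0.028 |
| 30% / 10% | 1 | 1.021 | 1.000 | 0.016 | 0.022 |

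At the design HR, equal rates give a difference of at most 0.629 − 0.626 = 0.003. Unequal rates give 0.627 − 0.614 = 0.013 towards tivozanib or 0.643 − 0.627 = 0.016 towards sorafenib. Under no effect, one-sided rejection with more NE on tivozanib is 0.039 against 0.028, with a Monte Carlo standard error of about 0.005.

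**Dependence on drop-out.** With 3% annual drop-out and 242 events (1,500 runs), the difference is below 0.001 at equal 10% rates and 0.011 to 0.013 at 30% versus 10%. The plan gives 3% per arm without a time unit.

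**Dependence on why a scan is NE.** A 600-run version assigned NE only to subjects already censored without PD. At 10% sorafenib / 30% tivozanib the HRs were 0.630 (SAP) and 0.640 (protocol), a gap of similar size in the same direction. Under no effect with 0% / 30% they were 0.997 and 1.020, so there the protocol rule is the one that shifts. That set-up assumes the unreadable scan would have shown no PD, which an NE reading cannot establish.

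**Does Sensitivity Analysis #4 cover it?** "This analysis will use the IRR assessments and backdate any PD events that occur immediately after missing or NE assessments". It needs a PD after the gap. A censored subject whose last scan is NE has none, so the date stays as it was.

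**The case against.** The SAP is silent on evaluability. A reader might infer a positive rule to censor whether or not the scan was evaluable, or that unread scans are credited. The documents support neither. The omission leaves the matter open, and Protocol 14.3.8 has two radiologists review every time point with third-reader adjudication, so the relevant category is not evaluable rather than unread.

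Bullet 1 applies only to a subject known to be alive and progression-free, which arguably excludes someone whose status is unknown at the last scan. That weakens bullet 1 as evidence. Bullets 2 and 3 have no such wording.

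The contrast with DoR might suggest a deliberate PFS rule. Only three of the five DoR bullets carry the qualifier, and the direct DoR counterpart of bullet 1 does not. Loose drafting is the likelier explanation, and the sponsor may well intend the protocol's rule. The SAP still does not say so, and the SAP is what gets programmed.

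Other sensitivity analyses bear on the issue. #1 uses investigator assessments, so it does not depend on IRR evaluability. #2 counts new anti-tumor treatment as an event, which removes bullet 2's censoring. #3 adds treatment discontinuation, which removes much of bullet 3's. They would help show whether the affected censoring drives the result. They do not correct the primary analysis, and #2 and #3 leave unchanged a subject still on treatment at cut-off with an NE last scan.

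**Conclusion.** The point stands as a gap between the two documents in the definition of the primary endpoint. All three scan-based PFS bullets drop the protocol's condition, nothing else in the SAP restores it for the primary analysis, and SAP 4.10 does not record a change.

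Its likely size is modest: 0.003 or less on the HR if NE rates are equal, and about 0.01 to 0.016 in either direction at 10% versus 30%. These figures rest on assumed NE rates, a fixed 8-week shift and, for the direction of bias, on NE being unrelated to true progression status. Planned sample size, event target and stated power are unaffected.

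Two larger claims are tempting. One is that every affected subject gains at least 8 weeks, but end-of-treatment and unscheduled scans can make the gain shorter. The other is a bigger HR shift from an extreme imbalance such as 50% versus 0%, for which the documents give no support. Nor do they show which arm would benefit.

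**What to change.** In all three PFS bullets of SAP 3.2.1, censor at the *last evaluable IRR tumor assessment documenting absence of PD*. State that a subject with no such assessment after randomization, and no PFS event, is censored at the randomization date.

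Choose one date convention. The protocol uses the day following the scan, the SAP's PFS bullets use the day itself, and the SAP's first DoR bullet uses the day following. The one-day difference is trivial, but the documents should agree. If the unqualified rule is really intended, list it in SAP 4.10 with a reason.

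The cost is a few words and one filter in the derivation of the censoring date. A count by arm of censored subjects whose last scan was NE would also show which scenario applies.
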